6 STUDY SCHEDULE

The schedule of the study is summarized at page [11](#).

6.1 Study visits and procedures

Each study subject will undergo 8 visits.

The study protocol foresees 2 periods separated by a wash-out interval of at least 14 days. Minimum study duration will be 20 days, screening visit included. A written informed consent will be obtained before any study assessment or procedure.

The first subject first visit (FSFV) is defined as the 1st visit performed at the Phase I Unit by the 1st screened subject. The last subject last visit (LSLV) is defined as the last visit performed at the Phase I Unit by the last subject, i.e. the last visit foreseen by the study protocol, independently of the fact that the subject is a completer or a withdrawn subject.

The following phases, visits and procedures will be performed:

▪ Screening phase

- Screening – visit 1: between day -21 and day -2
- Screening – visit 1.1: day -3 or day -2
- Period 1 – visit 2: day -1

▪ Interventional phase

- Period 1 – visit 3: days 1-4
- Wash-out interval of at least 14 days
- Period 2 – visit 4: day -3 or day -2
- Period 2 – visit 5: day -1
- Period 2 – visit 6: days 1-4

▪ Final phase

- Final visit/early termination visit (ETV). In case of early discontinuation, discontinued subjects will undergo an ETV.

	Day	Procedures/Assessments	Notes
Screening – Visit 1	From day -21 to day -2	
 ➤ Explanation to the subject of study aims, procedures and possible risks ➤ Informed consent signature ➤ Screening number (as S001, S002, etc.) ➤ Demographic data and life style recording ➤ Medical/surgical history ➤ Previous/concomitant medications ➤ Full physical examination (body weight, height, physical abnormalities) ➤ Vital signs measurement including blood pressure (BP), pulse rate (PR) and body temperature (BT) ➤ ECG recording ➤ Laboratory analyses: hematology, blood chemistry, urinalysis, serum virology and serum pregnancy test (women only) ➤ Alcohol breath test ➤ Urine multi-drug kit test ➤ AE monitoring ➤ Inclusion/exclusion criteria evaluation ➤ Eligibility evaluation 	Note: The first two letters of the surname followed by the first two letters of the first name will be used in the Phase I Unit source document only and will not be transferred to the Sponsor.
Screening – Visit 1.1	Day -3 or -2	
 ➤ Nasal and pharyngeal swab for SARS-COV2 test ➤ Adverse events monitoring ➤ Previous/concomitant medications 	
Period 1 - Visit 2	Day -1	
 ➤ Alcohol breath test ➤ Urine pregnancy test (women only) ➤ Urine multi-drug kit test ➤ ECG recording ➤ Vital signs measurement ➤ AE and concomitant medications ➤ Inclusion/exclusion criteria evaluation ➤ Eligibility evaluation ➤ Enrolment and randomization 	Arrival at the Phase I Unit in the evening. Confinement until the morning of day 4. Standardized low-fat dinner. Fasting for at least 10 h (overnight).

	Day	Procedures/Assessments	Notes
Period 1 - Visit 3	Day 1	
 ➤ Investigational medicinal product administration at 8:00 ± 1 h ➤ Vital signs measurement at pre-dose ➤ ECG recording at pre-dose ➤ Blood sample collection for PK analysis at pre-dose (0) and 0.25 (15 min), 0.5 (30 min), 1, 1.5, 2, 3, 4, 5, 6, 8, 10, 12 and 18 h post-dose ➤ AE and concomitant medications 	
Standardized high-fat and high caloric breakfast starting at 30 min pre-dose for subjects receiving the investigational medicinal product under fed conditions in this study period. Breakfast must be completed within 30 min. Subjects receiving the investigational medicinal product under fasting conditions will not have breakfast.
 
Standardized lunch and dinner at about 13:00 (5 h post-dose) and 20:00 (12 h post-dose), respectively

	Days 2 and 3	
 ➤ Blood sample collection for PK analysis at 24, 30, 36, 48, 54 and 60 h post-dose ➤ AE and concomitant medications 	Standardized breakfast, lunch and dinner at about 9:00, 13:00 and 20:00, respectively
	Day 4	
 ➤ Vital signs measurement upon discharge 72 h post-dose ➤ ECG recording upon discharge 72 h post-dose ➤ Blood sample collection for PK analysis at 72 h post-dose ➤ AE and concomitant medications ➤ Full physical examination (body weight and physical abnormalities) upon discharge 	
Discharge from the Phase I Unit in the morning, after the 72-h post-dose blood sample collection, ECG recording, vital signs check and full physical examination.
 
Upon leaving, the subjects will be instructed to contact immediately the investigator in case of occurrence of any adverse reactions.

Period 2 - Visit 4	At least 14 days	A wash-out interval of at least 14 days between the two administrations of the two study periods	
	Day -3 or -2	As visit 1.1, day -3 or -2	

	Day	Procedures/Assessments	Notes
Period 2 - Visit 5	Day -1	As visit 2, excluding enrolment and randomization. In addition full physical examination (body weight and physical abnormalities) will be performed.	As visit 2
Period 2 - Visit 6	Days 1-4	As visit 3. IMP administered according to the randomization list and crossover design	As visit 3
Final Visit/ETV	Day 4 of period 2 /at ETV in case of discontinuation	
 ➤ Full physical examination (body weight and physical abnormalities; also vital signs and ECG in case of ETV) ➤ Alcohol breath test ➤ Urine multi-drug kit test ➤ Laboratory analyses as at screening, with the exception of virology, coagulation, microbiology, albumin and globulin ➤ AEs and concomitant medications 
In case of clinically significant results at the final visit, the subjects will be followed-up by the investigator until the normalization of the concerned clinical parameter(s)
	Upon leaving, the subjects will be instructed to contact immediately the investigator in case of occurrence of any adverse reactions.

6.2 Diet and lifestyle

On day -1 of each period, a standardized low-fat dinner will be served after confinement. On day 1 of each study period, all the subjects will not take any food or drinks (except water) for at least 10 h (i.e. overnight). The subjects allocated to the fed conditions, after the overnight fasting period, will receive a high-fat and high-caloric breakfast (see § 6.2.1) starting 30 min pre-dose and will complete their breakfast within 30 min, while the subjects allocated to the fasting conditions will fast overnight and then receive their treatment. Water will be allowed as desired, except for 1 h before and 1 h after IMP administration. In order to maintain an adequate hydration, the subjects will be encouraged to drink at least 150 mL of still mineral water every 2 h for 5 h post-dose, starting at 1 h post-dose.

On day 1, all subjects will then remain fasted until 5 h post-dose. A standardized lunch and dinner will be served at approximately 5 h and 12 h post-dose (at approximately 13:00 and 20:00).

On days 2 and 3, standardized breakfast, lunch and dinner will be served to all subjects at about 9:00, 13:00 and 20:00, respectively.

One cup of coffee or tea will be allowed after each meal only; any other coffee, tea or food containing xanthines (i.e. coke, chocolate, etc.), alcohol and grapefruit will be forbidden

during confinement. In particular, grapefruit and alcohol will be forbidden for 24 h before the first IMP administration until the end of the study.

The subjects will be allowed to smoke 9 cigarettes during confinement, one after each meal, with the exclusion of the high-fat and high-caloric breakfast.

During confinement, routine ambulant daily activities will be strongly recommended.

6.2.1 Standardized high-fat and high-caloric breakfast

As mentioned above, on day 1 of each study period after blood sample collection at pre-dose (0), subjects randomized to the Test (T) treatment will start to eat a high-fat and high-caloric breakfast 30 min pre-dose and will be instructed to complete their meal within 30 min.

Breakfast caloric content will be approximately 1000 kilocalories (kcal) and fat content will be approximately 60% of the total caloric content. The standardized breakfast will provide approximately 15%, 25% and 60% of the calories from proteins, carbohydrates and fats, respectively, and is detailed in the table below:

Table 6.2.1.1 High-caloric and high-fat breakfast composition

Food	Amount (g)	Fats (g)	Carbohydrates (g)	Proteins (g)	kcal
Whole milk	250	8	12	8	160
Two fried eggs	140	14	1	13	180
Butter	30	25	0	0	227
Two strips of bacon	50	12	0	8	138
Two slices of toast	50	0	35	4	150
Olive oil white bread	40	2	20	4	100

6.2.2 Restrictions

During each study period, the subjects will be confined from the evening preceding the IMP administration (study day -1) until the morning of day 4.

For the 4 h following the administration, when not involved in study activities, the subjects will remain seated. They will not be allowed to lie down.

During confinement, hazardous, strenuous or athletic activities will not be permitted.

7 DESCRIPTION OF SPECIFIC PROCEDURES

7.1 Physical examination

Full physical examinations will be performed at:

- screening visit
- on day 4 of period 1 (before discharge)
- on day -1 of period 2
- final visit/ETV.

Body weight will be recorded each time. Subjects will be weighed (kg) lightly clothed without shoes. Height will be measured at screening only and BMI will be recorded. BMI will be calculated as weight [kg]/(height [m] x height [m]).

Information about the physical examination will be recorded by the investigator. Any abnormalities will be recorded.

Significant findings/illnesses, reported after the start of the study and that meet the definition of an AE (see § 11), will be recorded in the subject source documents.

Date of the physical examination, overall investigator's interpretation (as normal or abnormal and, if abnormal, clinically significant or not clinically significant) and clinically significant abnormalities (if any) will be reported in the individual electronic case report forms (eCRF).

7.1.1 Vital signs

Subjects' blood pressure (BP), pulse rate (PR) and tympanic body temperature (BT) will be measured by the investigator or his/her deputy after 5 min at rest in sitting position at:

- screening visit
- day -1
- day 1 at pre-dose (0)
- day 4 at 72 h post-dose (in period 2, it will be considered as the final visit measurement)
- ETV, if applicable

7.1.2 ECGs

12-Lead ECGs will be performed in supine position a:

- screening visit
- day -1
- day 1 at pre-dose (0)
- day 4 at 72 h post-dose (in period 2, it will be considered as the final visit recording)
- ETV, if applicable

Date/time of the ECG recording, overall investigator's interpretation (as normal or abnormal and, if abnormal, clinically significant or not clinically significant) and all abnormalities found (if any) will be reported in the individual eCRF.

7.1.3 Clinical laboratory assays

Samples of blood (17 mL) and urine will be collected. The following laboratory analyses will be performed at the screening visit at the clinical laboratory (§ 16.5):

Hematology

Leukocytes and leukocyte differential count (percentage values and absolute values), erythrocytes, hemoglobin (conv. units), hemoglobin (IS units), hematocrit, MCV, MCH, MCHC, thrombocytes,

Coagulation

Prothrombin time, aPTT

Blood chemistry

Electrolytes: sodium, potassium, calcium, chloride, inorganic phosphorus

Enzymes: alkaline phosphatase, γ -GT, AST, ALT

Substrates/metabolites: total bilirubin, creatinine, fasting glucose, urea, uric acid, total cholesterol, triglycerides

Proteins: total proteins, albumin, globulin (calculated by the laboratory by detracting albumin from total proteins)

Serum virology

Hepatitis B (HBs antigen), **Hepatitis C** (HCV antibodies), **HIV 1/2** (HIV Ag/Ab combo).

Urine analysis

Urine chemical analysis (stick): pH, specific weight, appearance, color, nitrites, proteins, glucose, urobilinogen, bilirubin, ketones, hematic pigments, leukocytes

Urine sediment (analysis performed only if positive): leukocytes, erythrocytes, flat cells, round cells, crystals, cylinders, mucus, bacteria

Microbiological analysis

Coronavirus SARS-COV-2 (nasopharyngeal swab) will be performed at the laboratory (§ 16.5) on day -3 or -2 of the visit 1.1 (screening visit) and on day -3 or -2 of period 2

A urine drug test will be performed at the Phase I Unit at screening, day -1 of each study period and final visit/ETV using a urine multi-drug kit. The following drugs will be assessed: cocaine, amphetamine, methamphetamine, cannabinoids (delta-9-tetrahydrocannabinol - THC), opiates and ecstasy.

A serum pregnancy test will be performed at the laboratory (§ 16.5) at screening and final visit/ETV. Urine pregnancy tests will be performed on day -1 of each study period at the Phase I Unit.

The same analyses, with the exception of coagulation, microbiology, albumin, globulin and virology will be performed at the final visit/ETV.

Date/time of samples collection, overall investigator's interpretation (as normal or abnormal and, if abnormal, clinically significant or not clinically significant) and all abnormalities found (if any) will be reported in the individual eCRF. All clinically significant abnormalities after the screening visit will be recorded as AEs.

7.2 Sampling for pharmacokinetic analysis

7.2.1 *Venous blood sampling*

Venous blood samples (8 mL) will be collected from a forearm vein at the following times:

- pre-dose (0), 0.25, 0.5, 1, 1.5, 2, 3, 4, 5, 6, 8, 10, 12, 18, 24, 30, 36, 48, 54, 60 and 72 h post-dose

Actual sampling times for each subject will be recorded in the individual electronic case report forms (eCRF). The actual sampling times should not exceed the recommended tolerance ranges presented in the table below. Any deviation outside the recommended ranges will be verified through Data Clarification Forms and, if confirmed, will be reported as protocol deviation, although it will not automatically lead to the exclusion of the concerned subjects from the PK Set.

Table 7.2.1.1 Tolerance ranges for the scheduled sampling times

Sampling time	Tolerance range
Pre-dose (0)	Within 40 min before IMP administration
0.25 h (15 min)	0 min
0.5 h (30 min)	± 1 min
1, 1.5 h	± 3 min
2, 3, 4, 5 h	± 5 min
6, 8, 10, 12, 18, 24, 30 h	± 10 min
36, 48, 54, 60, 72 h	± 30 min

Blood samples for PK analysis will be collected using an indwelling catheter with switch valve. The cannula will be rinsed, after each sampling, with about 1 mL of sterile saline solution containing 20 I.U./mL Na-heparin. The first 2 mL of blood will be discarded at each collection time to avoid contamination of the sample with heparin.

The remaining 6 mL will be collected from the catheter and transferred with a syringe into heparinized tubes (Li-heparin).

The samples will be stored on ice for a maximum of 15 min. Then the samples will be centrifuged at 4° C for 10 min at 2500 g to obtain plasma. Each plasma sample will be immediately divided into 3 aliquots, P1 (500 µL), P2 (500 µL) and P3 (the remaining amount), in pre-labeled polypropylene tubes, and stored frozen at ≤-20° C until shipment to the analytical laboratory.

If any clinical assessment, such as vital signs measurement or ECG recording, is foreseen at the same time-point as blood sampling for PK analysis, blood collection will be performed at the scheduled time. However, vital signs and ECG parameters can be influenced by the blood sampling. Therefore, these assessments can be performed within 30 min before the pre-dose

PK time point (0 h) and within 10 min before the other scheduled PK time-points. Any deviations outside the recommended time will be verified through Data Clarification Forms. However, since vital signs measurements and ECG recordings will be performed for safety reasons only, deviations from the planned time schedule will be considered not relevant.

7.2.2 *Analytics*

The concentration of DF 2156Y (total and unbound) and its metabolites (DF 2108Y and DF 2227Y) in plasma will be determined at Dompé farmaceutici S.p.A. Bioanalytical Laboratories, Italy, using a fully validated HPLC-UV method.

The concentrations of unbound DF2156Y will be determined initially only at the following time points: 1, 3, 6, 12, 24 h post dose: additional analysis could be performed at different time points only if necessary.

Analyses will be performed according to the general Principles of "OECD Good Laboratory Practices for testing of chemicals" C(81) 30 (final) and GCP.

The method validation report and the analytical report will be attached to the final clinical study report (CSR).

A total of 1512 plasma samples (756 samples for each study period) will be analyzed.

7.2.3 *Labeling, storage and transport of samples*

7.2.3.1 *Samples labeling*

Each sample tube will be clearly and unequivocally identified with a label resistant to the storage temperature and reporting:

Study code	Study CRO-PK-20-345 - Sponsor code LDX0219
Subject number	001-036
Tube identification	P1/P2/P3
Period	1/2
Scheduled sampling time	as h; see § 7.2.1 .

7.2.3.2 *Samples storage and transport*

At the Phase I Unit, the samples will be stored at $\leq -20^{\circ}$ C. At the end of each collection day, aliquots P1 will be stored in a freezer, separated from the other aliquots.

All aliquots P1, packed in sufficient solid CO₂, will be shipped by an authorized courier from CROSS Research S.A., Switzerland, to Dompé farmaceutici S.p.A. Bioanalytical Laboratories, Italy.

After receipt by the analytical laboratory of the first aliquots (P1) in good conditions, aliquots P2 will be shipped to the laboratory, applying the same procedures described for the shipment of aliquots P1.

All aliquots 1 and 2 will remain stored at the analytical laboratory (Dompé farmaceutici S.p.A. Bioanalytical Laboratories, Italy) at least until finalization of the CSR. Afterwards, the samples will be destroyed after authorization by the Sponsor's Project Manager and a confirmation of the disposal will be provided by email.

All aliquots P3 will remain stored ($\leq -20^{\circ}\text{ C}$) at CROSS Research S.A., Switzerland. These samples could either be:

- sent to the laboratory for reanalysis if necessary for analytical reasons or if any problems occur during the delivery of aliquots P1 and/or P2, or
- destroyed at an authorised site, or
- stored at CROSS Research S.A., for a maximum time of 5 years.

No analyses different from those stated in this protocol and agreed by the subjects when signing the informed consent form will be performed, unless a new informed consent and a new approval from the Ethics Committee is obtained. The subjects may ask to destroy their own samples at any time.

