Plasma samples were collected at pre-dose and 1, 2, 3, 4, 5, 6, 7, 8, 9, 10, 12, 16, 24, 36, 48, 60, 72, 84, 96, 120, 144 and 168 h post-dose. Urine samples were collected in the following time periods: 0-12, 12-24, 24-36, 36-48, and during subsequent intervals of 24 up to 168 h post-dose. Faces samples were collected in the intervals 0-24, 24-48, 48-72 and 72-96 h post-dose.

Main PK parameters of ladarixin and its metabolites measured and calculated after single dose of 400 mg of ladarixin are presented in the following table.

Table 1.4.2.1 PK parameters of ladarixin and its metabolites measured and calculated after single dose of 400 mg of ladarixin to healthy men (N=6)

Variable (Unit)	DF 2156Y (N=6)	DF 2108Y (N=6)	DF 2227Y (N=6)
C _{max} (µg/mL)	54.86±7.41	0.938±0.104	0.692±0.116
t _{max} (h)	1.75±1.12	14.92±772	45.98±15.91
AUC _{0-t} (µg/mL·h)	912.40±155.62	49.58±10.07	51.93±9.40
AUC _{0-∞} (µg/mL·h)	921.54±159.99	50.36±10.61	NC
t _{1/2} (h)	13.62±2.66	18.32±2.65	NC
V _z /F (L)	8.19±1.84	ND	ND
Cl/F (L/h)	0.42±0.07	ND	ND
Ae _{0-t} (% of dose)	79.67±9.99	2.00±0.45	1.08±0.33
Cl _R (L/h)	0.34±0.05	0.131±0.03	0.068±0.023
Ae _{Feces0-t} (µg)	120.76±52.31	0.0	0.0

mean±SD are reported; NC: not calculated; ND: not determined

1.4.3 Phase I safety, tolerability and bioavailability single and multiple dose study in healthy men

Twenty-four (24) men were randomized into 2 cohorts including 12 subjects (9 subjects received ladarixin and 3 subjects received placebo). Ladarixin was administered at the dose of 300 and 400 mg for 7 days. The subjects received a single dose on days 1 and 8 and twice daily every 12 h on days 3 to 7. Plasma samples were collected as follows:

Day 1: pre-dose and 0.5, 1, 1.5, 2, 3, 4, 5, 6, 8, 10, 12, 24 h post dosing

Day 3: Day 4, Day 5, Day 6: before the first and the second daily dosing

Day 7: before and 1h after the first and the second daily dose

Day 8: pre-dose and 0.5, 1, 1.5, 2, 3, 4, 5, 6, 8, 10, 12, 24, 36, 48, 60 and 72 h post dosing

Main PK parameters of ladarixin and its metabolites measured and calculated after single dose of 400 mg of ladarixin are presented in the following table.

Table 1.4.3.1 PK parameters of ladarixin and its metabolites measured and calculated after single dose of 400 mg of ladarixin to healthy men (N=9)

Variable (Unit)	DF 2156Y (N=9)	DF 2108Y (N=9)	DF 2227Y (N=9)
C_{\max} (µg/mL)	81.10±13.99	0.82±0.19	0.40±0.08
t_{\max} (h)	0.52 (0.50 – 1.52)	10 (8 – 12)	8.02 (5.02 – 12)

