2.2 Endpoints

2.2.1 *Primary end-point*

- to evaluate and compare the rate (C_{max}) and extent (AUC_{0-t} ; $AUC_{0-\infty}$) of absorption of DF 2156Y after single dose administration of 400 mg of ladarixin under fed and fasting conditions.

2.2.2 *Secondary end-points*

- to evaluate and compare between genders the rate (C_{max}) and extent (AUC_{0-t} ; $AUC_{0-\infty}$) of absorption of DF 2156Y and its metabolites (DF 2108Y and DF 2227Y) after single dose administration of 400 mg of ladarixin to healthy male and female volunteers;
- to describe the pharmacokinetic profile of DF 2156Y (total and unbound) and its metabolites (DF 2108Y and DF 2227Y) after single dose administration of 400 mg of ladarixin under fed and fasting conditions;
- to collect safety and tolerability data of a single oral dose administration of 400 mg of ladarixin.

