10.4 Analysis of pharmacokinetic parameters

10.4.1 Descriptive pharmacokinetics

A descriptive PK will be presented for plasma total and unbound DF 2156Y and its metabolites DF 2108Y and DF 2227Y. The results will be displayed and summarized in tables and figures. Individual and mean curves (+SD at sampling times), indicating inter-subject variability, will be plotted. Mean curves will be presented by treatment and by treatment and sex.

PK parameters of total plasma DF 2156Y and its metabolites DF 2108Y and DF 2227Y will be summarized by treatment and by treatment and sex.

Data below the lower quantification limit (BLQL) will be considered as 0 in the calculations and presented as BLQL in listings and tables. As a consequence of BLQL (i.e. 0) values, calculated geometric means (if requested) could be null. For this reason, in the presence of any null value, the geometric mean will be reported as NC. If for an individual PK curve, a log-linear regression with a correlation coefficient $R^2 > 0.8$ cannot be obtained, the extrapolated PK parameters will be reported as NC and considered missing in the calculations of descriptive statistics.

10.4.2 *Statistical comparison of pharmacokinetic parameters*

For the primary end-point evaluation of food effect, C_{max} , AUC_{0-t} and $AUC_{0-\infty}$ of total plasma DF 2156Y will be compared between fed and fasting conditions (T vs. R) using analysis of variance (ANOVA) for a cross-over design on log-transformed data for evaluation of the food effect. Period, treatment, sequence and subject within sequence will be taken in account as sources of variation and they will be treated as fixed effect.

The 90% confidence intervals (CI) will be calculated for the point estimates (PE, i.e. the T/R ratio of least square geometric means) of the PK parameters.

Established criteria for the absence of a food effect are that the 90% CI for the T/R ratio of the geometric means of the PK parameters under consideration are within the 80.00-125.00% range.

For the purpose of exploring the gender effect on bioavailability of ladarixin and its metabolites, following logarithmic transformation, C_{max} , AUC_{0-t} and $AUC_{0-\infty}$ of total plasma DF 2156Y and of DF 2108Y and DF 2227Y will be analyzed using ANOVA including sequence, period, treatment, subject within sequence, sex and sex*treatment interaction as fixed effect.

10.5 *Safety and tolerability evaluation*

➤ AEs

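### The initial unbound DF 2156Y assays start at 1 h, so the descriptive unbound profile has no value near the likely peak when absorption is rapid, although 0.5 h plasma is already drawn

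*Protocol*

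**What the plan says.** Section 2.2.2 lists as a secondary end-point "to describe the pharmacokinetic profile of DF 2156Y (total and unbound) and its metabolites (DF 2108Y and DF 2227Y") under fed and fasting conditions. Section 10.4.1 plans descriptive pharmacokinetics for total and unbound drug, with mean curves by treatment.

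Section 7.2.1 gives the blood sampling schedule as follows: "pre-dose (0), 0.25, 0.5, 1, 1.5, 2, 3, 4, 5, 6, 8, 10, 12, 18, 24, 30, 36, 48, 54, 60 and 72 h post-dose". Section 7.2.2 then says that unbound concentrations "will be determined initially only at the following time points: 1, 3, 6, 12, 24 h post dose", and adds that "additional analysis could be performed at different time points only if necessary". It does not say what would make them necessary.

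Section 1.4 gives two earlier 400 mg single-dose results:

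- Table 1.4.3.1 (9 men) gives t_max in hours as "0.52 (0.50 – 1.52"). Sampling there was "Day 1: pre-dose and 0.5, 1, 1.5, 2, 3, 4, 5, 6, 8, 10, 12, 24 h post dosing".
- Table 1.4.2.1 (6 men) gives t_max 1.75 ± 1.12 h. There, "Plasma samples were collected at pre-dose and 1, 2, 3, 4, 5, 6, 7, 8, 9, 10, 12, 16, 24, 36, 48, 60, 72" h and later.

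Neither study is described as fed or fasting.

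**The concern.** The study sets out to describe an unbound profile, yet its initial grid begins after the time at which the better-sampled earlier study found the peak of total drug. If absorption is as fast here, the unbound curve will start on its descending limb. The highest unbound concentration will be understated, and no unbound fraction will be obtained at the likely highest total concentration.

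If food slows absorption, the loss would fall mainly on the fasting period, and the plotted unbound peaks would look more alike, or more favourable to food, than they are. That step is an assumption, because the protocol gives no fed t_max. The plasma that would settle the matter is already being collected.

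**Working it through.** **Counts.** 36 subjects × 21 times = 756 samples per period, and × 2 periods = 1512. This reproduces the total in section 7.2.2. Initial unbound assays: 36 × 5 × 2 = 360.

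**Reading the two t_max values.** The footnote to Table 1.4.3.1 calls 0.52 h a mean. With nine values, minimum 0.50 and maximum 1.52, the mean is at least (8 × 0.50 + 1.52)/9 = 0.61 h, so 0.52 cannot be a mean. Read as a median, at least 5 of the 9 men had t_max at or before 0.52 h, that is, at about the first sample; the true peak may be earlier. The 1.75 h in Table 1.4.2.1 does not contradict this, because that study had no post-dose sample before 1 h.

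**Which model.** With V_z/F = 7.03 L, a one-compartment model cannot exceed 400/7.03 = 56.9 µg/mL. The same table reports C_max 81.10 µg/mL. A distribution phase after the peak is therefore needed.

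**Model.** C(t) = A·exp(−αt) + B·exp(−βt) − (A + B)·exp(−k_a·t)

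- From Table 1.4.3.1: C_max 81.10 µg/mL, AUC0-∞ 1063.2 µg/mL·h, t1/2 13.55 h, so β = ln 2/13.55 = 0.0512 per h.
- Assumed: distribution half-life 0.5 to 4 h (α = ln 2 divided by it); peak time t_p of 0.52, 0.4 or 0.3 h; unbound proportional to total, since no unbound fraction is given.
- Solved for A, B and k_a: C(t_p) = 81.10; C′(t_p) = 0; A/α + B/β − (A + B)/k_a = 1063.2.

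**Example.** For t_p = 0.52 h and a distribution half-life of 0.5 h, A = 91.14, B = 52.69 and k_a = 4.41. Then C(1) = 91.14 × 0.250 + 52.69 × 0.950 − 143.83 × 0.0122 ≈ 71.1, and 71.1/81.1 = 0.877.

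**Highest value on the grid as a share of the true peak** (range over distribution half-lives 0.5 to 4 h):

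| Assumed peak time | 1, 3, 6, 12, 24 h | with 0.5 h added |
|---|---|---|
| 0.52 h | 88–96% | about 100% |
| 0.4 h | 82–94% | 99–100% |
| 0.3 h | 78–93% | 94–98% |

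The present grid thus understates a 0.52 h peak by about 4 to 12%, and a 0.3 h peak by about 7 to 22%.

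**Later peaks.** For assumed peaks between 1.5 and 5 h, a one-compartment curve gives 96 to 100% capture on the present grid. This is only indicative, since that model does not reach the observed C_max. Adding 0.5 h does not help peaks between 1 and 3 h.

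**The case against.** The strongest reply has four parts.

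1. **No planned analysis uses an unbound peak.** Section 9.1 names no unbound C_max, t_max or AUC. Section 10.4.2 states that the parameters "of total plasma DF 2156Y will be compared between fed and fasting conditions (T vs. R"), and total drug is sampled at 0.25 and 0.5 h. This stands, and it limits the point to a descriptive secondary end-point.
2. **The grid is explicitly initial.** Further times may be assayed. Section 7.2.3.2 keeps the first two aliquots at least until the study report is final, and the third may be stored for up to 5 years. So nothing is lost for good, and the trigger might be set in a document not shown here. This stands in part: the protocol's wording permits the early assays but does not secure them.
3. **Early peaks are not uniform.** A mean of 1.75 h in the 6-man study requires at least one man to have peaked at the 2 h sample or later, and 1 h lies inside the range of the 9-man study. True, but this does not remove the early peaks in most of the nine.
4. **The size depends on assumed quantities.** Also true; hence the ranges.

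Three stronger readings are tempting, and the documents do not support them. A reader might take 0.52 h as a fasting t_max, but no feeding state is given. A reader might conclude that the fed and fasting unbound profiles cannot be compared, but the five times are identical in both periods and each can be compared. A reader might set C_max/AUC from the two earlier studies side by side (54.86/921.54 = 0.0595 against 81.10/1063.2 = 0.0763, 22% lower) and attribute the gap to starting at 1 h. Those are different small cohorts with different sampling, so the ratio does not isolate that effect.

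**Conclusion.** The point holds as a minor weakness in a descriptive secondary end-point. The initial unbound grid leaves out the time at which the better-sampled earlier study peaked. The likely understatement is about 4 to 12% of the peak for a 0.52 h peak, rising to about 22% at most for a 0.3 h peak. These figures rest on the assumed distribution half-life of 0.5 to 4 h, on the earlier study's kinetics applying here, and on unbound being proportional to total. If binding saturates at high concentrations, unbound drug would fall faster than total after the peak and the loss would be larger; the documents do not allow this to be quantified.

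That the loss falls mainly on the fasting period follows only if food delays absorption. The primary food-effect analysis is not affected.

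**What to change.** In section 7.2.2, add 0.5 h to the initial unbound set in both periods, giving 0.5, 1, 3, 6, 12 and 24 h. In the model this raises capture of a 0.52 h peak to about 100%, and of a 0.3 h peak to 94–98%.

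Cost: 36 × 2 = 72 more unbound assays (36 × 6 × 2 = 432 instead of 360) on plasma already collected, no extra blood draw, and one changed line of text.
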